1.2 Adverse Event and Serious Adverse Event Collection and Reporting

Adverse Events (AEs): Any untoward or unfavorable medical occurrence in a human subject, including any abnormal sign (for example, abnormal physical exam or laboratory finding), symptom, or disease, temporally associated with the subject's participation in the research, whether or not considered related to the subject's participation in the research. AEs encompass both physical and/or psychological harms.

Serious Adverse Events (SAEs): An adverse event that meets any of the following criteria:

- Results in death
- Is life threatening, or places the participant at immediate risk of death from the event as it occurred
- Requires prolonged hospitalization
- Causes persistent or significant disability or incapacity
- Is another condition which investigators judge to represent significant hazards

Unanticipated Problem: Any event, deviation, or problem, that meets ALL of the following criteria:

- a. Unexpected (see Expectedness definitions below) in terms of nature, severity, or frequency given (a) the research procedures that are described in the IRB-approved research protocol and informed consent document; and (b) the characteristics of the subject population being studied;
- b. Related or possibly related (see Relatedness definitions below) to participation in the research; and
- c. Suggests that the research places subjects or others at a greater risk of harm (including physical, psychological, economic, or social harm) than was previously known or recognized.

Adverse Events versus Unanticipated Problems:

- The vast majority of adverse events occurring in human subjects are not unanticipated problems.
- A small proportion of adverse events are unanticipated problems.
- Unanticipated problems include other incidents, experiences, and outcomes that are not adverse events.

Reporting: All AEs are collected on an Adverse Event Form in electronic format and recorded in the RedCap database. All AEs experienced by the participant from the start of intervention through the end of the study intervention period (6-months) will be reported to the Safety Officer (SO) and NIA in Safety Reports sent twice a year.

Unanticipated Problems Reporting: Unanticipated problems will be reported within 48 hours to NIA Program Officer and to the SO and will include a corrective plan and measures to prevent reoccurrence.

SAE Reporting: When SAEs occur that are unanticipated (i.e., events other than those described in the protocol, consent form and DSMP), and that are related to the intervention, they will be reported to NIA Program Officer and to the SO within 48 hours of study's knowledge of the SAE. The expedited report will be followed by a detailed, written SAE report as soon as possible. Follow up information may be required and asked for by the SO or the NIA.

Any anticipated AEs and SAEs will be reported in the bi-annual reports to the SO and NIA Program Officer.

Relatedness:

The potential event relationship to the study intervention and/or participation is assessed by the site investigator. The comprehensive scale to categorize an event is listed below:

- *Definitely Related:* The AE is clearly related to the investigational procedure – i.e. an event that follows a reasonable temporal sequence from administration of the study intervention, follows a known or expected response pattern to the suspected intervention, that is confirmed by improvement on stopping and reappearance of the event on repeated exposure and that could not be reasonably explained by the known characteristics of the subject's clinical state.
- *Possibly Related:* An AE that follows a reasonable temporal sequence from administration of the study intervention follows a known or expected response pattern to the suspected intervention, but that could readily have been produced by a number of other factors.
- *Not Related:* The AE is clearly not related to the investigational procedure - i.e. another cause of the event is most plausible; and/or a clinically plausible temporal sequence is inconsistent with the onset of the event and the study intervention and/or a causal relationship is considered biologically implausible.

Expectedness:

AEs must be assessed as to whether they were expected to occur or unexpected, meaning not anticipated based on current knowledge found in the protocol and the consent form. Categories are:

- *Unexpected:* The nature or severity of the event is not consistent with information about the condition under study or intervention in the protocol or consent form.
- *Expected:* The event is known to be associated with the intervention or population under study.

Classification of AE Severity:

- *Mild:* Awareness of signs or symptoms, but easily tolerated and are of minor irritant type causing no loss of time from normal activities. Symptoms do not require therapy or a medical evaluation; signs and symptoms are transient – i.e. no doctor visit or medical treatments were required.
- *Moderate:* Events introduce a low level of inconvenience or concern to the participant and may interfere with daily activities, but are usually improved by simple therapeutic measures; moderate experiences may cause some interference with functioning – i.e. minimal medical treatment was needed, possible doctor visit or physical therapy.
- *Severe:* Events interrupt the participant's normal daily activities and generally require systemic drug therapy or other treatment; they are usually incapacitating – i.e. medical attention was required, possible hospitalization.

Note: Severity is not synonymous with seriousness. SAEs are a subset of the reported AEs.

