2.2 Content Safety Report

At bi-annual intervals, the study team will prepare Safety Reports to be reviewed by the SO and NIA for recommendations for or against the trial's continuation, as well as any modification to the study. An open (i.e., not segregated by treatment) and closed (i.e., coded by treatment assignment (social dancing or treadmill walking)) report will be submitted to the SO. The contents of the reports will focus on patient accrual and demographics, data completeness, and other study performance measures. The closed report will additionally divide study participants according to treatment comparing participant demographics and baseline characteristics, rates and reasons for treatment discontinuation and loss to follow-up, and rates of serious adverse events. In addition, the PIs may prepare a section of the report addressing concerns they anticipate will have regarding the conduct of the study.

The reports will include:

- Monthly and cumulative accrual
- Baseline characteristics, overall and by treatment group
- Summary of completeness and quality of data collection forms
- Status of enrolled patients, overall and by treatment group
- Assessments of whether study personnel have followed eligibility criteria and other protocol requirements
- Assessment of participant adherence, overall and by treatment group
- Sample size assumptions
- Outcome rates, overall and by treatment group along with monitoring boundaries for efficacy and futility
- Listing of serious adverse events by participant ID number and a table of event-specific cumulative rates, overall and by treatment group
- A summary description of all adverse events

Only the closed report will include the comparisons by treatment group.

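### The SAE definition counts a hospital stay only if it is prolonged, a term left undefined, so an ordinary admission can fall outside the by-arm SAE tables

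*Combined protocol and SAP*

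**What the plan says.** DSMP section 1.2 makes an event serious if it meets any of five criteria: death; threat to life; "Requires prolonged hospitalization"; "Causes persistent or significant disability or incapacity"; or "Is another condition which investigators judge to represent significant hazards". The word prolonged is not defined there or elsewhere in the available text, and admission as such is not a criterion.

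Hospital care appears once more in section 1.2, in the severity scale. The severe grade is illustrated by "medical attention was required, possible hospitalization". The scale then carries a note: "Severity is not synonymous with seriousness. SAEs are a subset of the reported AEs".

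Section 2.2 sets out what the Safety Officer receives. The closed report compares the arms on "rates and reasons for treatment discontinuation and loss to follow-up, and rates of serious adverse events", as well as on baseline features. The list of contents includes "Listing of serious adverse events by participant ID number and a table of event-specific cumulative rates, overall and by treatment group". For adverse events in general the entry is "A summary description of all adverse events", with no split by arm stated.

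Sections 1.2 and 2.1 also require a report within 48 hours for SAEs that are both unanticipated and related to the intervention.

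**The concern.** Whether an event is serious decides how it is reported. SAEs receive rates, a listing and an event-specific table by treatment group; other adverse events are promised only a summary. A definition that turns on an undefined adjective lets two investigators classify the same short admission differently, each within the plan.

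The plan itself makes such admissions plausible. Participants are sedentary and aged 65 or older. Section 1.3 names falls and musculoskeletal injury as risks of the sessions and foresees emergency room referral. Under section 4, a recent cardiac event or stroke does not by itself exclude a person.

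At stake is whether the by-arm SAE tabulation counts admissions consistently. Safety is one of the feasibility metrics, and section 7 says the safety experience will inform the full-scale trial. A count that depends on how each investigator reads one word is hard to carry forward to that design.

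**Working it through.** The plan states no figure on this point, so there is none to reproduce. The check traces one hypothetical event through the rules.

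**The event.** A participant falls in a session, is admitted for two nights, recovers and returns to the programme.

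**Step 1: the five SAE criteria in section 1.2.**
- Death: no.
- Life-threatening: no, by construction.
- Prolonged hospitalization: undetermined, because no length is given. Read in its ordinary sense, two nights need not qualify.
- Disability or incapacity: persistent and significant are alternatives, so a temporary but significant incapacity could qualify. If the injury is minor, it does not.
- Investigator judgement of a significant hazard: open.

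If the disability criterion is not met and the stay is not read as prolonged, only the last item can make the event an SAE.

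**Step 2: does the severity scale settle it?** No. Hospitalization illustrates the severe grade, but the note under the scale separates severity from seriousness. A severe event with an admission can be non-serious under the plan.

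**Step 3: where the event appears, with and without the SAE label.**

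| Place | Classed as SAE | Not classed as SAE |
|---|---|---|
| Adverse event form and database (1.2) | yes | yes |
| Twice-yearly report to the Safety Officer and NIA, if during the 6-month intervention (1.2) | yes | yes |
| By-arm SAE rates (2.2) | yes | no |
| SAE listing and event-specific table by arm (2.2) | yes | no |
| 48-hour SAE report, if unanticipated and related (1.2, 2.1) | yes | no |
| 48-hour unanticipated-problem report, if its three conditions hold (1.2) | yes | yes |
| By-arm discontinuation reasons (2.2) | only if treatment stops | only if treatment stops |

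The label changes three rows. The 48-hour SAE row matters less for falls and musculoskeletal injuries. Section 1.2 treats events described in the protocol, consent form or DSMP as anticipated, and the DSMP describes both. The row bears mainly on other kinds of admission.

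**The case against.** The strongest reply is that little is lost. All adverse events are collected, and those during the intervention reach the Safety Officer twice a year. An admission that ends participation shows up by arm among the discontinuation reasons. The unanticipated-problem route runs to 48 hours without needing the SAE label, and it covers events unexpected in frequency. The disability criterion does not require permanence, and the severe grade is described as usually incapacitating, so many fall injuries needing admission could qualify that way. The amendment log adds that the definitions follow NIA policy.

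Most of this stands, and it limits the consequence. A reader might infer that the Safety Officer could miss an excess of admissions in one arm. The documents do not support that: with 32 participants and every intervention-period event reported, a few admissions would be visible in other parts of the reports.

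A reader might also attach a size. With 16 per arm, two admissions classed as non-serious would take an arm from 2/16 = 12.5% to 0/16 = 0%. That holds for any two events in an arm of 16 and says nothing about how often such admissions occur. The plan expects no serious events and cites fall rates below 1% in earlier programmes.

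The reply does not close the gap. Discontinuation reasons miss participants who return to sessions. The unanticipated-problem route needs unexpectedness, at least possible relatedness and a suggestion of greater risk than was known, all together. The NIA policy is not in the documents, so agreement with it cannot be checked; even if the wording agrees, the term is undefined here.

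**Conclusion.** The point holds as a matter of definition and tabulation. As written, an ordinary admission that meets neither the life-threatening nor the disability criterion is an SAE only by investigator judgement. If it is not judged so, it is absent from the by-arm SAE rates and event table, and from the 48-hour SAE report where that would have applied. It remains in the adverse event records and, for the intervention period, in the twice-yearly reports.

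No numerical size can be given, because the documents state no expected number of admissions. Nothing here affects the cognitive or imaging analyses. Nor do the documents show that seriousness would be judged differently between the arms; the issue is that the rule leaves room for inconsistency.

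The conclusion assumes that no text outside the available documents defines prolonged or adds admission as a criterion. Section 2.3 of the DSMP is not in the available text. The change is worth making because it is small and specific, not because monitoring would fail without it.

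**What to change.** In DSMP section 1.2, replace the hospitalization criterion with: *requires inpatient hospitalization or prolongs an existing hospitalization*. Any admission then enters the by-arm SAE rates and table without a judgement on length of stay. If participants have already been enrolled, apply the same wording to admissions already on adverse event forms, so that the count rests on one definition.

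As a complement, section 2.2 could state that the closed report tabulates all adverse events, or at least falls and admissions, by treatment group.

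The cost is a few more SAE forms in a 32-person trial, including some for admissions unrelated to the sessions, and approval of the revised DSMP. Participant care does not change.

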1.3 Protection Against Study Risks

Informed Consent Process:

- 1) The study interviewer will conduct the initial telephone-screening interview. Study interviewers will conduct an oral consent process over the telephone prior to asking any study related questions. Following the interview, potential subjects will be invited for further in-person evaluations. Study consent, evaluations, enrollment, and in-person interventions will be done at our research center.
- 2) The consent process will take place prior to initiating any study related evaluations or interventions and will inform a potential participant about the study. It indicates the participation is voluntary and he/she has the

right to stop at any time. Risks are enumerated in the informed consent form and described orally during the consent process.

Protection Against Risks:

The research staff and investigators will be present during all testing. All questionnaire completion will be done at a slow enough pace so as not to tire individuals. If participants express physical or mental tiredness or discomfort during any of the assessments or training procedures, the procedure will be terminated immediately. Drs. [name] or [name] will be available onsite or by cellular telephone at all times to address any safety concerns or clinical issues during the interventions.

- i) Falls: Recent dance interventions using similar protocols in cognitively healthy and impaired participants report no or low rate of falls during dance sessions.^{34, 107} The rate of falls was <1% among 5,500 participants from 11 diverse physical activity interventions participating in a trans NIH collaborative known as the Behavior Change Consortium.¹⁰⁸ A Cochrane review of interventions to promote physical activity reported that of the 8 physical exercise trials with information on adverse events, fall rates were only significantly different from controls in 1 out of these 8 studies.¹⁰⁹ Another Cochrane review that addressed the role of exercise programs (mostly walking but no dancing interventions) for people with dementia concluded that exercise was not harmful though the cognitive benefits were not proven.¹¹⁰

Despite the low fall rate in these previous reviews, we take safety seriously, and have instituted a number of procedures to minimize fall risk in our pilot trail. Both the dance and walking groups are closely supervised. The groups are small so that instructors can pay attention to the participants, and intervene if balance problems are noted during the session. Participants will be instructed to wear sports shoes with good grip soles. Footwear and clothing will be inspected by the instructors prior to the start of sessions to ensure that they are appropriate for both intervention activities. Wooden complaint flooring used in our dance space is associated with lower risk of fall injury than hard flooring, though not as low as carpeted wooden flooring.^{111, 112} However, carpets were reported to be associated with falls in a Cochrane review of studies.¹¹³ It would not be practical to have safety harnesses on participants in the dance group, and this has not been the practice in the multiple previous dance intervention studies. Participants in both groups will be frequently asked about their comfort/discomfort levels. The intervention will be stopped if participants report any unsteadiness or balance problems, and will be examined by the study clinician. Our research center is located within a hospital complex, and referral to primary care physician or emergency room will be done as required.

- ii) Musculoskeletal injuries: Given the sedentary nature of our participants, musculoskeletal symptoms or injuries may occur. Previous studies suggest that though musculoskeletal complaints are common in physical activity interventions, the majority of these issues are mild in nature.¹⁰⁸ Both the dance and walking groups are closely supervised. The groups are small so that instructors can pay attention to the participants. Participants are frequently asked about their comfort/discomfort levels including the Borg scale. The intervention will be stopped if participants report any discomfort, and will be examined by the study clinician. Our research center is located within a hospital complex, and referral to primary care physician or emergency room will be done depending on the severity of the problem.
- iii) Neuroimaging results: [name] will be immediately contacted in the event that an acute imaging finding requiring immediate action is discovered. She will review the reports of all MRI studies. Participants with normal studies will receive a letter to this effect. In the event that a non-urgent significant abnormality is discovered, [name] will contact the participant by telephone to discuss the findings and advise that appropriate follow-up be obtained. A follow-up letter summarizing the discussion will be sent to the participant. If the participant wishes, the report will be sent to the primary care doctor.

- iv) MRI Safety program: A comprehensive MRI safety program is in place including secure access to the MRI suite and ongoing surveillance for effectiveness of the safety program. A board certified subspecialty neuroradiologist will review each MRI scan for pathology and confirm that there are no clinically significant findings for any of the participants. All data are archived in the Picture Archival and Communication System (PACS) and if needed can be archived in DVD-R media and stored in a locked cabinet.

2.0 Data and Safety monitoring

All data collection in this clinical trial will be monitored to assure subject comfort, safety, and confidentiality. The clinical trial protocols, data collection instruments, subject recruitment letters, and consent forms will be reviewed and approved by the IRB. The NIA will also approve the creation and structure of the DSMP.

The PIs will be responsible for ensuring participants' safety on a daily basis. The SO will advise the NIA Program staff and the PIs regarding participant safety, participant risks and benefits, scientific integrity and ethical conduct of a study.

2.1 Frequency of Data and Safety Monitoring

Safety Reports will be sent to the SO twice a year and will include a detailed analysis of study progress, data and safety issues.

All deaths will be reported within 24 hours of study's knowledge of death. The report of death will be submitted to the NIA Program Officer and to the SO. When SAEs occur that are unanticipated and that are related to the intervention, they will be reported to NIA Program Officer and to the SO within 48 hours of the study staff's knowledge of SAE. The summary of all other SAEs will be reported in Safety Reports bi-annual reports.

2.2 Content Safety Report

At bi-annual intervals, the study team will prepare Safety Reports to be reviewed by the SO and NIA for recommendations for or against the trial's continuation, as well as any modification to the study. An open (i.e., not segregated by treatment) and closed (i.e., coded by treatment assignment (social dancing or treadmill walking)) report will be submitted to the SO. The contents of the reports will focus on patient accrual and demographics, data completeness, and other study performance measures. The closed report will additionally divide study participants according to treatment comparing participant demographics and baseline characteristics, rates and reasons for treatment discontinuation and loss to follow-up, and rates of serious adverse events. In addition, the PIs may prepare a section of the report addressing concerns they anticipate will have regarding the conduct of the study.

The reports will include:

- Monthly and cumulative accrual
- Baseline characteristics, overall and by treatment group
- Summary of completeness and quality of data collection forms
- Status of enrolled patients, overall and by treatment group
- Assessments of whether study personnel have followed eligibility criteria and other protocol requirements
- Assessment of participant adherence, overall and by treatment group
- Sample size assumptions
- Outcome rates, overall and by treatment group along with monitoring boundaries for efficacy and futility
- Listing of serious adverse events by participant ID number and a table of event-specific cumulative rates, overall and by treatment group
- A summary description of all adverse events

Only the closed report will include the comparisons by treatment group.

